Abbreviations used in this table may be found in Appendix 12 .														
 Day relative to start of study intervention (Day 1). Baseline (Day 1) visit is a mandatory visit. Assessments indicated in brackets [X] are only to be conducted if indicated as described in the “Notes”. 	
Visit Window	Day -1 to Day 1	0 days	±1 day	±1 day	±1 day	±2 days	±2 days	±2 days	±3 days	±7 days	±7 days	±5 days		
 Screening procedures may be done from Day -1 to Day 1 and may be completed on the same calendar day as Baseline/Day 1 procedures. If screening and baseline visits are conducted on the same calendar day, assessments and procedure that are listed to occur at both visits only need to be completed once. 	
														
 screening and baseline, the baseline estimate of kidney function will determine eligibility. See Section 8.3.2.4. 	
FSH	X													
 FSH is to be performed locally to confirm postmenopausal status in female participants <60 years of age at screening who are not using hormonal contraception or hormonal replacement therapy. Female participants aged 50 to 60 years with no menses for 12 months do not need FSH testing to be performed to confirm postmenopausal status. See Appendix 2. 	
HIV test (Germany only)	X													
 Local HIV testing at screening will be performed for participants in Germany as required by the German HA See Appendix 2 See Section 8.3.4. 	
Pregnancy Test	X								X			X			
SARS-CoV-2 Serology		X		X				X				X			
Biomarker Assessments															
NP swab collection for SARS-CoV-2 RNA level		X	X	X	X	X	X	X	X			X		
 All NP swabs of both nares, will be collected by HCP at visits indicated. Samples will be shipped to central lab for quantitative SARS-CoV-2 RNA concentration. 	

Table 1. Study Schedule of Assessment

Visit Identifier	Screen	Treatment Period			Efficacy and Safety Follow-up Period						LTFU			Notes
		Baseline (Day 1)	Day 3	Day 5	Day 10	Day 15	Day 21	Day 28	Day 34	Week 12	Week 24	ET (prior to Day 34)		
Abbreviations used in this table may be found in Appendix 12 .														
 Day relative to start of study intervention (Day 1). Baseline (Day 1) visit is a mandatory visit. Assessments indicated in brackets [X] are only to be conducted if indicated as described in the “Notes”.

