	
remains below the LLOQ through Day 34 for participants with NP swab SARS-CoV-2 RNA greater than or equal to the LLOQ at baseline.
 
 Rebound in SARS-CoV-2 RNA level in NP swabs at follow-up (ie, any study visit from Day 10 to through Day 34, defined as a half (0.5) \log_{10} copies/mL increase or greater in SARS-CoV-2 RNA level relative to SARS-CoV-2 RNA level on Day 5 and with a follow-up viral RNA level $\geq 2.5 \log_{10}$ copies/mL. 	

 To compare the effect of nirmatrelvir/ritonavir on the rate of cell culture infectious virus over time in participants with mild-to-moderate COVID-19 	
In participants with detectable viral titers at baseline by TCID50:
 
 Time to negative infectious titer by TCID50. Change in TCID50 from baseline to Days 3, 5, 10, 15, 21, 28, and 34. Proportion of participants with negative infectious titer by TCID50 on Days 3, 5, 10, 15, 21, 28, and 34. 
In participants with positive viral titers at baseline by virus recovery:
 
 Time to negative infectious titer by virus recovery. Proportion of participants with negative infectious titer by virus recovery on Days 3, 5, 10, 15, 21, 28, and 34. 	
 Not applicable

 To compare the effect of nirmatrelvir/ritonavir to placebo/ritonavir on viral concentration in plasma in participants with mild-to-moderate COVID-19. 	
 Change from baseline in SARS-CoV-2 viral RNA level in plasma, over time. 	
 Not applicable.

 To compare the effect of nirmatrelvir/ritonavir to placebo/ritonavir on COVID-19-related hospitalization and all-cause mortality in participants with mild-to-moderate COVID-19. 	
 Proportion of participants with COVID-19-related hospitalization > 24 h or death from any cause through Day 28. 	
 Not applicable.

 To compare the effect of nirmatrelvir/ritonavir to placebo/ritonavir on COVID-19-related healthcare resource utilization in participants with mild-to-moderate COVID-19. 	
 Number of COVID-19-related medical visits through Day 34. 	
 Not applicable.

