6.3. Tertiary/Exploratory Endpoints

6.3.1. Proportion of Participants with SARS-CoV-2 RNA in NP Swab below the LLOQ on Days 3, 5, 10, 15, 21, 28, and 34

The number and proportion of participants with SARS-CoV-2 RNA level in NP swabs $<2.0 \log_{10}$ copies/mL at 3, 5, 10, 15, 21, 28, and 34 will be summarized by treatment group. The analysis will be done using mITT analysis set.

6.3.2. Proportion of Participants with Sustained NP Swab SARS-CoV-2 RNA below the LLOQ (defined as $<2.0 \log_{10}$ copies/mL) from Day 5 through Day 34

The number and proportion of participants with sustained NP swab SARS-CoV-2 RNA $<$ LLOQ (defined as $<2.0 \log_{10}$ copies/mL) from Day 5 through Day 34 will be summarized by treatment group using mITT analysis set.

Sustained SARS-CoV-2 RNA below the LLOQ from Day 5 through Day 34 is defined as having all non-missing measurements from Day 5 to Day 34 below the LLOQ and no more than 3 visits with missing SARS-CoV-2 RNA levels (scheduled collection on Days 5, 10, 15, 21, 28 and 34).

6.3.3. Proportion of Participants with SARS-CoV-2 RNA in NP Swabs below the LLOQ (defined as $<2.0 \log_{10}$ copies/mL) on both Days 5 and 10

The number and proportion of participants with SARS-CoV-2 RNA in NP swabs below the LLOQ (defined as $<2.0 \log_{10}$ copies/mL) on both Days 5 and 10 will be summarized by treatment group. The analysis will be done using mITT analysis set.

6.3.4. Change in SARS-CoV-2 RNA Level in NP Swabs from Baseline to Days 3, 10, 15, 21, 28, and 34

Change in SARS-CoV-2 RNA level in NP swabs from baseline to Days 3, 10, 15, 21, 28, and 34 will be analyzed similarly to the primary endpoint using MMRM model in the mITT analysis set. The LS means and treatment difference for each visit will be calculated and presented with their corresponding 95% CIs.

6.3.5. Time to Sustained NP Swab SARS-CoV-2 RNA below the LLOQ (defined as $<2.0 \log_{10}$ copies/mL) and Remains below the LLOQ through Day 34 for Participants with NP Swab SARS-CoV-2 RNA Greater than or Equal to the LLOQ at Baseline

Time to sustained NP swab SARS-CoV-2 RNA below the LLOQ (defined as $<2.0 \log_{10}$ copies/mL) and remains below the LLOQ through Day 34 will be summarized graphically using Kaplan-Meier plots for each of the treatment groups. The analyses will be done similarly as in Section 6.2.2 using the mITT analysis set, which includes participants with baseline viral load \geq LLOQ.

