Sustained is defined as NP swab SARS-CoV-2 RNA level not $\geq 2.0 \log_{10}$ copies/mL at any study visit (through Day 34) following the first study visit where the participant's NP swab SARS-CoV-2 RNA $<$ LLOQ.

Let t represent the study day t between Day 5 and 28 visit inclusive for which there is a measurement of SARS-CoV-2 RNA level.

Then a sustained event will correspond to the first possible value of t to satisfy the following criteria:

- a) The Day t SARS-CoV-2 RNA level is $<$ LLOQ
- b) At least one SARS-CoV-2 RNA measurement is $<$ LLOQ after Day t
- c) All available (non-missing) SARS-CoV-2 RNA measurements between Day t and Day 34 visit are $<$ LLOQ
- d) No more than 50% missingness between Day t and Day 34 are missing.

There are limitations to the timing of the first event date as NP viral RNA is generally only captured at scheduled visits during the study.

The Day 28 visit is the last possible day the sustained NP swab SARS-CoV-2 RNA $<$ LLOQ can be achieved.

The time to the sustained event is defined as:

- For a participant with sustained event at Day t , the First Event Date is the date of the Day t measurement, and time to event will be calculated as (First Event Date) – (First Dose Date) +1.
- For a participant for which no possible value of $t \leq$ the Day 28 visit satisfies the criteria for a sustained event (censored), censoring date will be the date of the last available protocol-specified SARS-CoV-2 RNA measurement other than Day 34 visit, and time will be calculated as (Censoring Date) – (First Dose Date) +1.

6.3.6. Rebound in SARS-CoV-2 RNA Level in NP Swabs at Follow-up ie, Any Study Visit from Day 10 to through Day 34, Defined as a Half (0.5) Log₁₀ Copies/mL Increase or Greater in SARS-CoV-2 RNA Level Relative to SARS-CoV-2 RNA Level on Day 5 and with a Follow-up Viral RNA Level ≥ 2.5 Log₁₀ Copies/mL

The number and proportion of participants with rebound in SARS-CoV-2 RNA level in NP swabs up at follow-up will be summarized by treatment group. The analyses will be done using mITT analysis set.

In addition, two alternative definitions of rebound will also be evaluated:

- Rebound that is defined as: SARS-CoV-2 RNA level in NP swabs at follow up (ie, any study visit after Day 5 through Day 34) that is defined as a half (0.5) log₁₀ copies/mL increase or greater in SARS-CoV-2 RNA level relative to SARS-CoV-2 RNA level on Day 5, with a follow-up viral RNA level ≥ 3.0 log₁₀ copies/mL.

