Appendix 2. Data Derivation Details

Appendix 2.1. Definition and Use of Visit Windows in Reporting

The following table defines the visit windows and labels for viral RNA data and infectious titer data:

Visit Label	Target Day	Visit Window
Baseline (Day 1)	Day 1	Days -1 to 1
Day 3	Day 3	Days 2 to 4
Day 5	Day 5	Days 4 to 7
Day 10	Day 10	Days 8 to 12
Day 15	Day 15	Days 13 to 17
Day 21	Day 21	Days 18 to 24
Day 28	Day 28	Days 25 to 30
Day 34	Day 34	Days 31 to 37

The following table defines the visit windows and labels for vital sign data:

Visit Label	Target Day	Visit Window
Baseline (Day 1)	Day 1	Days -1 to 1
Day 3	Day 3	Days 2 to 4
Day 5	Day 5	Days 4 to 7
Day 10	Day 10	Days 8 to 21
Day 34	Day 34	Days 22 to 37

The following table defines the visit windows and labels for Lab data:

Visit Label	Target Day	Visit Window
Baseline (Day 1)	Day 1	Days -1 to 1
Day 5	Day 5	Days 2 to 19
Day 34	Day 34	Days 20 to 37

These visit windows will be applied to visit-wise summary and may be revised for analysis and reporting purpose when deemed appropriate.

For viral RNA data collected in NP swab or plasma, and vital sign data collected on study Day 4, it has falls into Day 3 visit and Day 5 visit due to an overlap between Day 3 and Day 5 visit windows, the decision made is to assign the window according to the nominal visit. If the nominal visit is “ET” visit, it will be assigned to Day 5 visit.

For lab data, if there are multiple measurements on the same day, the average will be used.

For vital sign data, if there are multiple measurements on the same day, the latest measurement will be used.

For viral RNA data collected in NP swab or plasma and infectious titer data, if there are multiple measurements on the same day, the largest value will be used.

For rapid antigen test data, if there are multiple measurements with negative and positive results on the same day, the positive result will be used.

If two or more measurements fall into the same visit window, keep the one closest to the Target Day. If two measurements are equal distance from the Target Day in absolute value, the later visit should be used.

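### SAP 6.3.5 counts sustained clearance from the first visit below LLOQ, but its event rule cannot start before the Day 5 visit, so clearance sustained from the Day 3 swab is dated late

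*SAP*

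**What the plan says.** SAP 6.3.5 gives a definition and then an event rule.

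- **Definition.** Clearance is sustained if RNA is not at or above 2.0 log10 copies/mL "at any study visit (through Day 34) following the first study visit" at which the participant is below LLOQ. No earliest visit is named.
- **Event rule.** "Let t represent the study day t between Day 5 and 28 visit inclusive for which there is a measurement of SARS-CoV-2 RNA level". The event is the earliest t that meets four criteria: (a) Day t is below LLOQ; (b) at least one later measurement is below LLOQ; (c) all available measurements through Day 34 are below LLOQ; (d) "No more than 50% missingness between Day t and Day 34 are missing". The event date is the date of the Day t swab.
- **Stated limits.** The section mentions "limitations to the timing of the first event date as NP viral RNA is generally only captured at scheduled visits" and gives the Day 28 visit as the last possible event visit. It gives no reason for starting at Day 5.

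The Protocol Section 3 endpoint also sets no earliest day. It asks when RNA falls below LLOQ and "remains below the LLOQ through Day 34 for participants with NP swab SARS-CoV-2 RNA greater than or equal to the LLOQ at baseline". In the Schedule of Activities (Protocol 1.3), the row "NP swab collection for SARS-CoV-2 RNA level" is marked at Day 3. SAP Appendix 2.1 gives Day 3 its own viral RNA window (Days 2 to 4), and SAP 6.3.1 reports the proportion below LLOQ at Day 3. SAP 2.1 declares no modification to the protocol's analysis.

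**The concern.** Definition and rule disagree for one group: participants already below LLOQ at the Day 3 swab who stay there. By the definition and the protocol endpoint their clearance begins at Day 3. By the rule it cannot begin before the Day 5 visit.

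The Kaplan-Meier curves therefore cannot step at Day 3. In the Cox model that SAP Appendix 1 lists for this endpoint, participants cleared from Day 3 are merged with those first cleared at Day 5. At stake is how accurately one exploratory endpoint shows early clearance.

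**Working it through.** The plan states no figure for this rule, so there is none to reproduce. The check applies the rule twice, with t starting at Day 5 and at Day 3, and compares the results.

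**Inputs.** Scheduled post-baseline NP swabs: Days 3, 5, 10, 15, 21, 28, 34 (Protocol 1.3). Criteria a to d, with Day 28 as the last allowed t (SAP 6.3.5). Windows: Day 3 visit = Days 2 to 4, Day 5 visit = Days 4 to 7, Day 10 visit = Days 8 to 12 (SAP Appendix 2.1).

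**Patterns.** Each of the 7 swabs is below LLOQ, at or above LLOQ, or missing: 3^7 = 2187 patterns.

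**Which patterns change.** The start day matters only if Day 3 itself qualifies as t: Day 3 below LLOQ, no later swab at or above LLOQ, and criterion d met from Day 3.

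- Day t counted: 7 visits, so at most 3 missing (3/7 = 43%, 4/7 = 57%).
- Only visits after Day t counted: 6 visits, so at most 3 missing (3/6 = 50%, 4/6 = 67%).

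Both readings allow 0 to 3 of the 6 later swabs to be missing: 1 + 6 + 15 + 20 = 42 patterns.

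**Where a Day 5 start puts them.**

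| Criterion d | Day 5 | Day 10 | Day 15 | Day 21 | Day 28 | No event | Total |
|---|---|---|---|---|---|---|---|
| Day t counted | 26 | 11 | 4 | 1 | 0 | 0 | 42 |
| Only visits after Day t | 16 | 11 | 4 | 3 | 1 | 7 | 42 |

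The readings part where 3 later swabs are missing. Example: Days 3, 5, 10 and 15 below LLOQ; Days 21, 28 and 34 missing.

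- From Day 3, both readings give an event at Day 3 (3/7 or 3/6 missing).
- From Day 5 with Day t counted, 3/6 = 50% are missing, so the event is at Day 5.
- From Day 5 with Day t not counted, 3/5 = 60% fails. At Day 10, 3/4 = 75% fails. At Day 15 no later swab exists, so criterion b fails. The participant is censored.

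**Size of the date shift.** With all swabs present the only shift is to the Day 5 visit: 5 − 3 = 2 nominal days. Across the windows it is 1 day (adjacent days) to 7 − 2 = 5 days. If the Day 5 swab is missing and the event falls at Day 10, the shift is 7 nominal days, from 8 − 4 = 4 to 12 − 2 = 10.

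**Scale.** The documents give no Day 3 clearance rate. As an illustration only, assume that 1% of an arm clears from Day 3 with all swabs present and no censoring before the Day 5 visit. The cumulative curve is then 1 percentage point lower between the two visits than with a Day 3 start, and mean time to event is 0.01 × 2 = 0.02 days longer (0.01 to 0.05 across the windows). The Day 3 count in SAP 6.3.1 will be an upper bound on the number affected.

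**A second mismatch.** Take Day 3 below, Day 5 above, Day 10 onward below. Read literally, the definition says not sustained, because a value at or above LLOQ follows the first visit below it. The rule gives an event at Day 10 from either start day.

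**The case against.** The strongest reply is that the executable rule is clear: a programmer has one start day to code. Protocol 9.3.4 leaves exploratory definitions to the SAP, so protocol silence on an earliest day is not in itself a conflict. Day 5 is also a recurring anchor: sustained clearance from Day 5 (6.3.2), clearance at Days 5 and 10 (6.3.3), rebound relative to Day 5 (6.3.6). On this view the floor may be deliberate, and a clause in the definition would cure it.

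Part of this stands. A Day 5 start would be a coherent choice, so the remedy can go either way. But 6.3.2, 6.3.3 and 6.3.6 name Day 5 in the endpoint itself and 6.3.5 does not. Delegation to the SAP also cannot reconcile two statements within one SAP section.

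A second reply is that few participants may be affected. The 7-patient rebound series in Protocol 2.1 had a range of 4.2 to 7.3 log10 copies/mL, so even its lowest value would have to fall by more than 4.2 − 2.0 = 2.2 log10 by Day 3. That is indicative only: the series is tiny, and the SAP uses a baseline category below 4.

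The overlap noted in SAP Appendix 2.1 ("it has falls into Day 3 visit and Day 5 visit due to an overlap between Day 3 and Day 5 visit windows") does not explain the floor. Day 4 samples are assigned by nominal visit, with ET samples going to Day 5, so Day 3 remains a distinct visit.

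A reader might infer that everyone below LLOQ at Day 3 is redated. That is not so: a later value at or above LLOQ, or 4 or more of the 6 later swabs missing, makes the start day irrelevant.

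**Conclusion.** The inconsistency is real and minor. Clearance sustained from Day 3 that meets criteria b to d from Day 3 is dated at the Day 5 visit when all swabs are present, nominally 2 days late against the section's own definition. With swabs missing, it is dated at Day 5 or later.

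Whether the floor can also remove events depends on criterion d: none of the 42 patterns if Day t is counted, 7 if it is not. The SAP does not settle this, so neither result can be presented alone. The counts assume scheduled swabs only and say nothing about how often each pattern occurs.

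A reader might infer a biased hazard ratio, lost power or a threat to the trial's main conclusions. The documents support none of these. They give no Day 3 clearance rate in either arm, the endpoint is exploratory and outside the testing sequence in SAP 5.1, and Day 3 results are still reported in 6.3.1 and 6.3.4.

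**What to change.** Before unblinding, in SAP 6.3.5:

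1. Let t run between the Day 3 visit and the Day 28 visit inclusive, which matches the definition and the protocol endpoint. If a Day 5 start is intended, the definition and the endpoint label should instead say that clearance is counted from the Day 5 visit.
2. State in criterion d whether Day t is counted. Counting it matches 6.3.2, which allows "no more than 3 visits with missing SARS-CoV-2 RNA levels (scheduled collection on Days 5, 10, 15, 21, 28 and 34"), that is, 3 of 6 with the starting visit included. It may change event status for other participants. With Day 3 at or above LLOQ, Days 5, 10 and 15 below and the rest missing, there is an event at Day 5 if Day t counts (3/6) and censoring if it does not (3/5).
3. Reword the definition as the first visit below LLOQ after which no available measurement through Day 34 is at or above LLOQ, so that it agrees with the rule's earliest qualifying t when an initial clearance is transient.

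Cost: three wording edits and a small change to the derivation program; no new data. The drawback of a Day 3 start is that it no longer matches the Day 5 start in 6.3.2.

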- Rebound that is defined as: SARS-CoV-2 RNA level in NP swabs at follow up (ie, any study visit after Day 5 through Day 28) that is defined as a half (0.5) log₁₀ copies/mL increase or greater in SARS-CoV-2 RNA level relative to SARS-CoV-2 RNA level based on Day 5, with a follow-up viral RNA level ≥ 3.0 log₁₀ copies/mL.

The rebound analyses will be restricted to those participants with non-missing SARS-CoV-2 RNA measurement on DAY 5 and at least one non-missing measurement among after Day 5 visit through the Day 34 visit (or through the Day 28 visit for the second alternative definition of rebound analysis).

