Proportion of participants with SARS-CoV-2 RNA in NP swabs below the LLOQ (defined as <2.0 log ₁₀ copies/mL) on both Days 5 and 10	Exploratory	mITT	Missing data will not be imputed.	Descriptive summary

Endpoint	Analysis Type	Population	Data Inclusion and Rules for Handling Intercurrent Events and Missing Data	Analysis Model
Change in SARS-CoV-2 RNA level in NP swabs from baseline to Days 3, 10, 15, 21, 28, and 34	Exploratory	mITT	MMRM method to take account of missing at random.	MMRM
Time to sustained NP swab SARS-CoV-2 RNA below the LLOQ (defined as $<2.0 \log_{10}$ copies/mL) and remains below the LLOQ through Day 34	Exploratory	mITT	Missing data will not be imputed.	Cox proportional hazard model; KM curves
Rebound in SARS-CoV-2 RNA level in NP swabs at follow-up (ie, any study visit after Day 5 to through Day 34, defined as a half (0.5) \log_{10} copies/mL increase or greater in SARS CoV-2 RNA level relative to SARS-CoV-2 RNA level on Day 5 and with a follow-up viral RNA level $\geq 2.5 \log_{10}$ copies/mL	Exploratory	mITT	Missing data will not be imputed.	Descriptive summary

Endpoint	Analysis Type	Population	Data Inclusion and Rules for Handling Intercurrent Events and Missing Data	Analysis Model
Rebound in SARS-CoV-2 RNA level in NP swabs at follow-up (ie, any study visit after Day 5 to through Day 34, defined as a half (0.5) log ₁₀ copies/mL increase or greater in SARS CoV-2 RNA level relative to SARS-CoV-2 RNA level on Day 5 and with a follow-up viral RNA level $\geq 3\log_{10}$ copies/mL	Exploratory	mITT	Missing data will not be imputed.	Descriptive summary
Rebound in SARS-CoV-2 RNA level in NP swabs at follow-up (ie, any study visit after Day 5 to through Day 28, defined as a half (0.5) log ₁₀ copies/mL increase or greater in SARS CoV-2 RNA level relative to SARS-CoV-2 RNA level on Day 5 and with a follow-up viral RNA level $\geq 3\log_{10}$ copies/mL	Exploratory	mITT	Missing data will not be imputed.	Descriptive summary
Change from baseline in SARS-CoV-2 viral RNA level in plasma, over time	Exploratory	mITT	MMRM method to take account of missing at random.	MMRM
Proportion of participants with COVID-19-related hospitalization	Exploratory	mITT	Missing data will not be imputed.	Descriptive summary

Endpoint	Analysis Type	Population	Data Inclusion and Rules for Handling Intercurrent Events and Missing Data	Analysis Model
>24h or death from any cause through Day 28				

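### The RNA-rebound proportions in SAP 6.3.6 count participants with one non-rebounding early swab as rebound-free through Day 34 (or Day 28), so the rate among those included can only be understated

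*SAP*

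**What the plan says.** SAP 6.3.6 defines rebound as a rise of at least 0.5 log10 copies/mL over the Day 5 value, with a floor on the follow-up level. The main definition uses a floor of 2.5 and looks at "Any Study Visit from Day 10 to through Day 34". Two alternatives use a floor of 3.0 and run through Day 34 and Day 28.

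The estimator is a simple count and percentage: "The number and proportion of participants with rebound in SARS-CoV-2 RNA level in NP swabs up at follow-up will be summarized by treatment group".

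The denominator has two conditions. The first is "The rebound analyses will be restricted to those participants with non-missing SARS-CoV-2 RNA measurement on DAY 5". The second is "at least one non-missing measurement among after Day 5 visit through the Day 34 visit", or "or through the Day 28 visit for the second alternative definition of rebound analysis". No minimum number of swabs and no late visit is required. SAP Appendix 1 lists all three rebound rows as descriptive summaries and states "Missing data will not be imputed".

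Two neighbouring endpoints do address sparse follow-up. SAP 6.3.2 lists "scheduled collection on Days 5, 10, 15, 21, 28 and 34" and allows at most 3 missing visits before a participant can be called sustained below the LLOQ. SAP 6.3.5 carries the condition "No more than 50% missingness between Day t and Day 34 are missing".

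**The concern.** A rebound percentage through Day 34 reads as a statement about people watched through Day 34. Under this rule some may have been watched only to Day 10. Their unobserved period is scored as free of rebound, although the SAP never says so in words: it follows from a crude proportion over that denominator with nothing imputed.

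Two things are at stake. The rate is pulled down in each arm to the extent that swabs are missing. If late swabs are more complete in one arm, the arms can differ with no true difference behind it. The two alternative definitions are also affected: they differ only in horizon, so a missing Day 34 swab narrows the gap between them for a reason unrelated to virology.

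The pattern is plausible. The Schedule of Activities collects an NP swab at early termination, and SAP Appendix 2.1 assigns viral RNA from study Days 8 to 12 to the Day 10 visit. A participant who leaves at that time can supply exactly the one swab needed to qualify.

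**Working it through.** The documents give no rate, sample size or power for rebound, so there is no planned figure to reproduce.

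**Direction.** Five NP swabs are scheduled after Day 5 (Days 10, 15, 21, 28, 34). The event is rebound at any of them. For an included participant, removing a swab can turn a rebound into a non-rebound and never the reverse. The observed proportion is therefore at or below the proportion the same people would show with complete swabs.

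**One participant under three rules.** Take someone below the LLOQ on Days 5 and 10 with no swab afterwards.
- SAP 6.3.2: four visits are missing, more than the 3 allowed, so not sustained.
- SAP 6.3.5: taking t as Day 5, four of the five later visits are missing, which exceeds 50%. Taking t as Day 10, no later measurement exists. There is no event, and the participant is censored.
- SAP 6.3.6: in the denominator, counted as no rebound through Day 34.

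**Size, as an illustration.** Let r be the rebound proportion with complete swabs, m the share of the denominator whose only later swab is Day 10, and f the share of rebounders first detectable after Day 10. Assume m and f are independent. Then

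observed = r × (1 − m × f).

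For r, Protocol 2.1 gives EPIC-HR rates of persistent rebound and, in addition, transient rebound: 2.32% + 4.65% = 6.97% on nirmatrelvir/ritonavir and 1.73% + 2.35% = 4.08% on placebo. The documents give neither m nor f; the ranges of 5% to 30% and 25% to 75% are assumptions.

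| r | m | f | m × f | observed | shortfall (points) |
|---|---|---|---|---|---|
| 6.97% | 5% | 25% | 0.0125 | 6.88% | 0.09 |
| 6.97% | 15% | 50% | 0.075 | 6.45% | 0.52 |
| 6.97% | 30% | 75% | 0.225 | 5.40% | 1.57 |
| 4.08% | 5% | 25% | 0.0125 | 4.03% | 0.05 |
| 4.08% | 15% | 50% | 0.075 | 3.77% | 0.31 |
| 4.08% | 30% | 75% | 0.225 | 3.16% | 0.92 |

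On the planned 210 evaluable active participants, the largest of these is 0.0157 × 210 = 3.3 people.

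**Unequal completeness.** With r = 6.97% in both arms and f = 50%, m = 5% gives 6.97% × 0.975 = 6.80% and m = 20% gives 6.97% × 0.90 = 6.27%. That is a difference of 0.52 points with no true effect.

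**Does censoring help?** In the scenario r = 6.97%, m = 15%, f = 50%, the risk at Day 10 is 0.0697 × 0.5 = 0.03485. Among those without rebound and still followed, the later risk is 0.03485 / 0.96515 = 0.03611. The Kaplan-Meier estimate is 1 − 0.96515 × (1 − 0.03611) = 0.0697. It recovers the full 6.97%, where the crude proportion gives 6.45%.

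**The case against.** The strongest reply is that little depends on this table. Rebound is tertiary, descriptive, has no estimand and lies outside the Type I error hierarchy. That is right and limits the weight of the point.

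Markedly unequal missingness is also not the natural expectation. The trial is double-blind, both arms receive ritonavir, dosing ends by Day 5 or 6, visits may take place at the participant's location, and early termination triggers a swab. The documents give no ground to predict an arm imbalance, so the spurious difference is a possibility only. SAP 6.3.1 and 6.3.4 also show the late viral course visit by visit, and SAP 6.5.2 reports disposition by arm. These help a reader, but they do not correct the rebound percentage.

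The 50% condition in SAP 6.3.5 and the visit limit in 6.3.2 belong to event definitions. They stop sparse data from creating a success; they do not remove people from a denominator. They show that the plan regards thin follow-up as a problem, but they are not a precedent for restricting the denominator here.

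Three stronger readings are tempting and not supported. A reader might infer that anyone lacking follow-up is scored as rebound-free; in fact participants with no swab after Day 5 are excluded, and a single swab that shows rebound is counted as rebound. A reader might infer that the table measures the outcome that prompted the trial; the rationale is symptom rebound with a positive antigen test, and Protocol 2.1 calls the clinical relevance of RNA increases unknown. A reader might take a large bias as established; the documents do not show one.

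**Conclusion.** The point holds as a modest, inexpensive improvement to an exploratory analysis. The direction is certain for those included: missed swabs can only lower the reported rate. The size cannot be found from the documents. Over the assumed ranges it is about 0.1 to 1.6 points at r = 6.97% and about 0.05 to 0.9 points at r = 4.08%, or 1.2% to 22.5% in relative terms. It is zero if swabs are complete or if no rebound falls at a missed visit.

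These figures rest on independence of missingness and rebound timing, and on EPIC-HR rates from a first course, where rebound was observed on Day 10 or Day 14. They illustrate scale and do not forecast this trial. The primary and key secondary tests are unaffected.

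**What to change.** Amend SAP 6.3.6 and the matching rows of Appendix 1 as follows.

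1. For each definition, report cumulative incidence of first rebound by scheduled visit (Kaplan-Meier or life-table), by arm, with the Day 34 or Day 28 estimate and its 95% CI. Censor participants without observed rebound at their last available swab within the horizon.
2. Keep the crude proportion, and beside it report the number of post-Day 5 swabs by arm.
3. Add a sensitivity proportion that keeps every observed rebounder and applies a completeness requirement, for example at least 50% of post-Day 5 swabs, only to participants without observed rebound. Applying the requirement to everyone would discard real events.
4. State that this sensitivity proportion leans upward. With r = 6.97%, m = 15%, f = 50%, the numerator is 0.06447, the participants removed are 0.15 × (1 − 0.03485) = 0.14477, and the result is 0.06447 / 0.85523 = 7.54%.

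The cost is SAP wording and one extra table, with no new data. Two limits should be stated with the results: the cumulative incidence assumes that dropout is unrelated to rebound, and it does not recover rebounds at visits missed between two attended ones. The second matters because Protocol 2.1 reports transient rises as more frequent than persistent ones.
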